3.2.1. IgG Concentration

Concentrations of anticapsular IgG for the 20 pneumococcal serotypes (1, 3, 4, 5, 6A, 6B, 7F, 8, 9V, 10A, 11A, 12F, 14, 15B, 18C, 19A, 19F, 22F, 23F, and 33F) will be determined in all subjects at all time points using the Luminex assay. Results will be reported as IgG concentrations.

Antibody concentrations above the LLOQ are considered accurate and their quantitated values will be reported. Values below the LLOQ, denoted as below the limit of quantification (BLQ), will be set to $0.5 \times LLOQ$ for analysis.

To support the secondary endpoints, geometric mean concentrations (GMCs) will be calculated and summarized for 1 month after Dose 3 and 1 month after Dose 4.

[figure not shown]
Proportions of subjects with serotype-specific IgG concentrations equal to or above the reference concentrations noted below will be calculated.

Serotype-specific IgG reference concentrations are defined below.

- ≥0.35 µg/mL will be used for serotypes 1, 3, 4, 6A, 7F, 8, 9V, 10A, 11A, 12F, 14, 15B, 18C, 19F, 22F, 23F, and 33F.
- \geq 0.23 µg/mL will be used for serotype 5.
- \geq 0.10 µg/mL will be used for serotype 6B.
- $\geq 0.12 \,\mu \text{g/mL}$ will be used for serotype 19A.

3.4. Baseline and Other Variables

Baseline variables include the following data as part of the baseline characteristics:

- Demographics
- Medical history
- Physical examination

Other variables to be summarized include:

- E-diary completion
- Prior/concomitant vaccines

3.4.1. Demographics, Medical History and Physical Examination

The demographic variables are age at first vaccination (in days), sex, race, and ethnicity. Age at first vaccination in days will be derived as (1st vaccination date – date of birth + 1).

For subjects assigned to receive vaccine, but who are not vaccinated, the enrollment date will be used in place of the date of first vaccination

Medical history will be categorized according to the Medical Dictionary for Regulatory Activities (MedDRA).

A physical examination will be performed. It will evaluate any clinically significant abnormalities within the following body systems: general appearance; skin; head, eyes, ears, nose, and throat; heart; lungs; abdomen; musculoskeletal; extremities; neurological; and lymph nodes. Clinically significant abnormal results will be recorded in the CRF.

3.4.3. Prior/Concomitant Vaccines and Concomitant Medications

The subject may receive vaccines with inactivated poliovirus, hepatitis B, or *Haemophilus influenzae* type b (either separately or in combination with diphtheria, tetanus, and pertussis antigens) at 2, 4, and 6 months of age, Measles, mumps, and rubella (MMR) vaccine may be administered concomitantly at 12 months of age with Dose 4 or more than 1 month after Dose 4. Rotavirus vaccine may be administered orally at any time. Vaccines licensed and recommended for this age group other than the combination diphtheria, tetanus, and pertussis combination vaccine may be administered with 20vPnC or 13vPnC, or as specified in the protocol.

Concomitant medications will be recorded only if they were used to treat SAEs and NDCMCs. Concomitant and prior vaccines, and concomitant medications will be coded using the World Health Organization (WHO) Drug Dictionary (WHODD).

3.5. Safety Endpoints

Local reactions, systemic events, antipyretic/pain medication, AEs, SAEs and NDCMCs have been described above in the primary endpoints.

4. ANALYSIS SETS

Data for all subjects will be assessed to determine if subjects meet the criteria for inclusion in each analysis population prior to each analysis planned for this study (see Section 7). Classifications will be documented per standard operating procedures.

See Appendix 1.1 for an outline of handling protocol deviations.

4.1. Safety Analysis Population

The **overall safety population** will include all subjects who receive at least 1 dose of study vaccine (20vPnC or 13vPnC) and have safety data reported in the study. Subjects will be assigned to vaccine group corresponding to the vaccine actually received. The safety population will be the analysis population for safety and reactogenicity endpoints.

Separate safety populations will be defined for each vaccination as follows:

Dose 1 to Dose 3 Safety Population - Subjects receiving Dose 1 and having safety data between Dose 1 and the blood draw visit 1 month after Dose 3

Dose 4 Safety Population - Subjects receiving Dose 4 and having safety data between Dose 4 and 6 months after Dose 4

If a subject's actual vaccine dose varies within a particular safety population (eg, overall or Dose 1 to Dose 3), the subject data will be either analyzed for any by-dose presentation, or data will be presented in listings as appropriate.

4.2. Evaluable Immunogenicity Populations

The evaluable immunogenicity population will be defined for Dose 3 and Dose 4 separately.

The Dose 3 evaluable immunogenicity population will include any subject:

- 1. Who was eligible for the study.
- 2. Who was randomly assigned to receive the vaccine.
- 3. Who was 42 to 98 days of age, inclusive, on the day of first vaccination.
- 4. Who received the vaccine to which he or she was randomly assigned at the first 3 doses.
- 5. Who had a valid and determinate IgG concentration for at least 1 serotype from 1 month after Dose 3 visit (Visit 4).
- 6. Whose blood collection was within 27 to 56 days, inclusive, after Dose 3.
- 7. Who received no prohibited vaccines before the blood draw at 1 month after Dose 3.
- 8. Who had no other major protocol deviations as determined by the clinician or medical monitor.

The Dose 3 evaluable immunogenicity population will be the primary analysis population for immunogenicity results from the blood collected at 1 month after Dose 3.

The Dose 4 evaluable immunogenicity population will include any subject:

- 1. Who was eligible for the study.
- 2. Who was randomly assigned to receive the vaccine.
- 3. Who was 42 to 98 days of age, inclusive, on the day of first vaccination.
- 4. Who received the assigned vaccine, as randomized, within the defined window for Dose 4 (365-386 days of age; see Protocol Schedule of Activities).
- 5. Who received the vaccine to which he or she was randomly assigned at all 4 doses.
- 6. Who had a valid and determinate IgG concentration for at least 1 serotype after Dose 4.
- 7. Whose blood collection was within 27 to 56 days, inclusive, after Dose 4.
- 8. Who received no prohibited vaccines before the blood draw at 1 month after Dose 4.
- 9. Who had no other major protocol deviations as determined by the clinician or medical monitor.

The Dose 4 evaluable immunogenicity population will be the primary analysis population for immunogenicity results before and after Dose 4.

The blood collection window has been expanded by 1 extra day before, and 14 days after (see #6 above located under the Dose 3 evaluable immunogenicity population definition and #7 above for the Dose 4 evaluable immunogenicity population definition) the protocol-specified blood collection window of 28 to 42 days defined in the protocol, for consistency with established rules in the Prevnar 13 development program.

Subjects will be summarized according to their randomized vaccine in the immunogenicity analysis based on evaluable immunogenicity populations.

5. GENERAL METHODOLOGY AND CONVENTIONS

5.1. Hypotheses

No hypothesis testing will be performed, and also no formal statistical decision rules apply in this study. A descriptive estimation approach will be used to assess all safety and immunogenicity objectives. Nominal 95% confidence intervals will be calculated for all proposed endpoints.

5.2. General Methods

Time points for local reactions and systemic events refer to data within 7 days of each dose.

5.2.1. Analyses for Binary Data

Descriptive statistics for categorical variables (eg, proportions) are the percentage (%) and the numerator (n), the denominator (N) used in the percentage calculation, with 95% CIs.

The exact 95% confidence interval (CI) for binary endpoints will be computed using the F distribution (Clopper-Pearson 1). If r is the number of responses and n is the number of subjects, then it follows that p = r/n is the estimate of the proportion of response. An exact 95% CI can be computed by solving the following 2 equations. For the lower limit p_{I} ,

$$p_L = \frac{rF_L}{(rF_L + (n-r+1))}$$

and for the upper limit p_U ,

$$p_U = \frac{(r+1)F_U}{(n-r) + (r+1)F_U}$$

[figure not shown]
where F_L is the quantile from the F distribution for α =0.025, with numerator degrees of freedom equal to 2r and denominator degrees of freedom equal to 2(n-r+1). F_U is the quantile from the F distribution for α =0.975, with numerator degrees of freedom equal to 2(r+1) and denominator degrees of freedom equal to 2(n-r). When r equals 0, F_L should be set equal to 1.0 so p_L equals 0. When r equals n, F_L should be set equal to 1.0 so p_U equals 1.0.

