### 3.3. Number of Subjects

Approximately 460 subjects will be randomized (230 subjects per arm). Assuming a 15% dropout rate, approximately 200 subjects would be evaluable for immunogenicity. Subjects who withdraw or are withdrawn from the study after randomization will not be replaced, regardless of the reason for withdrawal.

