### 9.3. Immunogenicity Analysis

All serotypes will be analyzed in the same way. All endpoints will be summarized by vaccine group.

The Luminex assay IgG concentration of 0.35 µg/mL will be used as the predefined IgG

reference concentration for all serotypes, with the exception of serotypes 5 (0.23  $\mu g/mL$ ), 6B (0.1  $\mu g/mL$ ), and 19A (0.12  $\mu g/mL$ ). The 95% CIs will be obtained using the Clopper-Pearson method.

[figure not shown]

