6.2. Secondary Endpoints

The ordering of the pneumococcal serotypes in summaries will be as follows and will appear on the same table:

- 13vPnC serotypes: 1, 3, 4, 5, 6A, 6B, 7F, 9V, 14, 18C, 19A, 19F, 23F; and
- Additional Serotypes: 8, 10A, 11A, 12F, 15B, 22F, 33F.

6.2.1. Pneumococcal Serotype-specific Immunoglobulin G (IgG) Concentrations 1 Month after Dose 3

Endpoint: Pneumococcal serotype-specific IgG concentrations 1 month after Dose 3

- Time points: 1 month after Dose 3
- Analysis population: Dose 3 evaluable immunogenicity
- Analysis methodology: Descriptive statistics
- Supporting objective: Secondary Objective

Reporting results:

IgG GMCs with their associated 95% CIs will be summarized separately at 1 month after Dose 3 for each pneumococcal serotype by each vaccine group.

The percentage (%) and the number of subjects with serotype-specific IgG concentrations \geq reference concentrations (n) and the denominator (N) used in the percentage calculation, and corresponding 95% Clopper-Pearson CI will be presented for each vaccine group 1 month after Dose 3.

6.2.2. Pneumococcal Serotype-specific Immunoglobulin G (IgG) Concentrations 1 Month after Dose 4

[figure not shown]
Endpoint: Pneumococcal serotype-specific IgG concentrations 1 month after Dose 4

[figure not shown]
- Time points: 1 month after Dose 4
- Analysis population: Dose 4 evaluable immunogenicity CCI
- Analysis methodology: Descriptive statistics
- Supporting objective: Secondary Objective

Reporting results:

IgG GMCs with their associated 95% CIs will be summarized separately at 1 month after Dose 4 for each pneumococcal serotype by each vaccine group.

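### The SAP's Clopper-Pearson rule for 100% responders (r = n) probably names the wrong quantile: it overrides F_L, which is valid there, and leaves F_U undefined

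*SAP*

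**What the plan says.** SAP 5.2.1 states that "The exact 95% confidence interval (CI) for binary endpoints will be computed using the F distribution" and gives one equation for each limit:

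- p_L = r·F_L / (r·F_L + (n − r + 1)), where F_L is the 0.025 quantile of F with 2r and 2(n − r + 1) degrees of freedom.
- p_U = (r + 1)·F_U / ((n − r) + (r + 1)·F_U), where F_U is the 0.975 quantile of F with 2(r + 1) and 2(n − r) degrees of freedom.

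Two boundary rules follow. For no responders: "When r equals 0, F_L should be set equal to 1.0 so p_L equals 0". For all responders: "When r equals n, F_L should be set equal to 1.0 so p_U equals 1.0". The section has no other rule for F_U.

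The method is named elsewhere too. Protocol 9.3 says "The 95% CIs will be obtained using the Clopper-Pearson method", Protocol 9.4 names Clopper-Pearson for the safety proportions, and SAP 6.1 and 6.2.1 repeat it. SAP 5.1 says "Nominal 95% confidence intervals will be calculated for all proposed endpoints".

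**The concern.** The stated result cannot follow from the stated action, because F_L appears only in the equation for p_L. Setting it to 1.0 cannot make p_U equal 1.0.

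The r = 0 rule shows what the pattern should be. It overrides F_L because the numerator degrees of freedom of F_L, 2r, are then zero. At r = n the quantile with zero degrees of freedom is F_U (denominator 2(n − r) = 0). The second rule should therefore override F_U, and the sentence has probably carried over the subscript from the one before it.

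The study tests no hypotheses, so these intervals are its only formal expression of uncertainty. A likely place for r = n is the percentage at or above the IgG reference concentration 1 month after Dose 3, which SAP 6.2.1 reports for 20 serotypes in two vaccine groups. The documents give no expected response rates, so it is an assumption that 100% cells will occur.

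**Working it through.** **Inputs.** The equations, quantiles and boundary rules are those of SAP 5.2.1. Protocol 9.1 gives 230 infants per arm. Protocol 3.3 says that, after 15% dropout, "approximately 200 subjects would be evaluable for immunogenicity". It does not say whether this is per arm. Since 230 × 0.85 = 195.5, I read it as per arm and use n = 195, 200 and 230.

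**Step 1: the SAP's equations away from r = n.** Coded as written and compared with the beta-quantile form of Clopper-Pearson, they agree for every r from 0 to n − 1 at n = 20, 195 and 230 (largest difference 3 × 10⁻¹⁶). At n = 200, the r = 0 rule gives 0% to 1.83% for 0/200. The general equations and the r = 0 rule are correct.

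**Step 2: r = n, as written.** At n = 200, F_U is the 0.975 quantile with 402 and 0 degrees of freedom. This does not exist (software returns a missing value), so p_U is undefined. Setting F_L = 1 gives p_L = 200·1 / (200·1 + 1) = 200/201 = 0.99502.

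**Step 3: r = n, correct lower limit.** F_L is the 0.025 quantile with 400 and 2 degrees of freedom, which is 0.26859. Then

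p_L = 200 × 0.26859 / (200 × 0.26859 + 1) = 53.718 / 54.718 = 0.98172.

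This equals 0.025^(1/200), the closed form for r = n. It is also the mirror image of the SAP's own 0/200 result: 1 − 0.01828 = 0.98172.

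**Step 4: r = n with the subscript changed.** Setting F_U = 1 gives p_U = (n + 1) / (0 + (n + 1)) = 1.0, exactly the value the SAP says it wants.

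**Step 5: size of the error if p_U is hard-coded to 1.0 and F_L is still overridden.**

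| Cell | Correct p_L = 0.025^(1/n) | p_L with F_L = 1, n/(n + 1) | Difference (points) |
|---|---|---|---|
| 195/195 | 98.13% | 99.49% | 1.36 |
| 200/200 | 98.17% | 99.50% | 1.33 |
| 230/230 | 98.41% | 99.57% | 1.16 |

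At the wrong limit for 200/200, the probability of seeing all 200 respond is (200/201)^200 = 0.369. An exact 95% interval puts its lower limit where that probability is 0.025.

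**The case against.** The strongest reply is that this is a slip in an explanatory note about a named standard method. The sentence itself states the required upper limit. A statistician who asks standard software for a Clopper-Pearson interval gets the right answer and never uses the note. The silent error needs several things at once: hand-coded F formulas, p_U fixed at 1.0, F_L overridden although it plays no part in p_U, no comparison with a standard routine, and a cell with 100% responders. Nothing in the documents suggests the first four. All of this stands, and it limits the weight of the point.

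The second reply is that the case rests on one subscript, which may have been misread in the PDF text. The same section shows another misread subscript: the lower-limit symbol appears once as p_I where the equation has p_L. A misread therefore cannot be excluded. But that slip is L for I on a different symbol. The disputed F_L reads cleanly, as do the p_U in the same sentence and the other F_L and F_U symbols in the section. The doubt justifies checking the source page first; it does not remove the point.

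**Conclusion.** The concern holds, as a minor one. As it reads, the r = n rule in SAP 5.2.1 overrides a quantile that is valid and gives no rule for the one that is undefined.

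There are two possible consequences. One is a missing upper limit, which anyone checking the table would notice. The other is a lower limit between 1.16 and 1.36 points too high at the sample sizes planned here, which looks plausible and could pass unnoticed. Both are confined to cells with r = n, and both need the formulas to be coded by hand from the note. Point estimates, all intervals with r < n, the r = 0 rule and the intended upper limit of 1.0 are sound. No decision rule changes.

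The conclusion assumes that the subscript in the source SAP is the one shown. The figures for n = 195 and 200 also assume that the evaluable number in Protocol 3.3 is per arm.

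**What to change.** 1. Check the subscript in the r = n sentence against the source SAP.
2. If it reads as shown, change that sentence to set F_U, not F_L, to 1.0 so that p_U is 1.0. State that F_L keeps its 0.025 quantile, with 2n and 2 degrees of freedom.
3. Add a boundary test to the table program: 200/200 should return 98.17% to 100%, the mirror of 0/200 (0% to 1.83%).

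The cost is one symbol and a short clause in the SAP, and one test case.

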5.2.2. Analyses for Continuous Data

Unless otherwise stated, descriptive statistics for continuous variables are n, mean, median, standard deviation, minimum, and maximum.

5.2.2.1. Geometric Mean (GM)

Geometric means will be computed along with associated 95% CIs. The GM will be calculated as the mean of the assay results after making the logarithm transformation and then back transformation to its original scale. Two-sided 95% CIs will be obtained by taking log transforms of concentrations, calculating the 95% CI with reference to the t-distribution, then exponentiating the confidence limits.

5.3. Methods to Manage Missing Data

For the analysis of safety endpoints, the sponsor data standard rules for imputation will be applied (eg., partial dates for AEs will be imputed according to Pfizer standard algorithms).

Methods for handling missing local reactions and systemic events are described in Section 3.1 CCI

Methods for handling IgG concentrations CCI below the limit of quantitation are described in Section 3.2 CCI All immunogenicity analyses will be performed after the imputation of the IgG concentrations CCI that are below the LLOQ. Missing immunogenicity values will be retained as missing.

6. ANALYSES AND SUMMARIES

6.1. Primary Endpoints

6.1.1. Local Reactions

6.1.1.1. Primary Analysis

Endpoints: Proportions of subjects reporting prompted local reactions (redness, swelling, and pain at the injection site) within 7 days of each dose

- Analysis time points: Within 7 Days Dose 1; Within 7 Days Dose 2; Within 7 Days Dose 3; Within 7 Days – Dose 4
- Analysis population: Dose 1 to Dose 3 safety population for Doses 1 to 3, Dose 4 safety population for Dose 4
- Analysis methodology: Descriptive statistics
- Supporting objective: Primary Objective

Reporting results:

Proportions of subjects reporting prompted local reactions will be summarized by maximum severity level. The percentage (%) and the numerator (n) and the denominator (N) used in the percentage calculation, and corresponding 95% Clopper-Pearson CI will be presented for each vaccine group at all time points. The same descriptive statistics will be compiled across all 4 doses.

6.1.2. Systemic Events

6.1.2.1. Primary Analysis

Endpoints: Proportions of subjects reporting prompted systemic events (fever, decreased appetite, irritability, and drowsiness/increased sleep) within 7 days of each dose.

- Analysis time points: Within 7 Days Dose 1; Within 7 Days Dose 2; Within 7 Days Dose 3; Within 7 Days Dose 4
- Analysis population: Dose 1 to Dose 3 safety population for Doses 1 to 3, Dose 4 safety population for Dose 4
- Analysis methodology: Descriptive statistics
- Supporting objective: Primary Objective

Reporting results:

The percentage (%) and the numerator (n) and the denominator (N) used in the percentage calculation, and corresponding 95% Clopper-Pearson CI will be presented for each vaccine group at all time points. The same descriptive statistics will be compiled across all 4 doses.

6.1.3. Adverse Events

6.1.3.1. Primary Analysis

Endpoint: Proportions of subjects reporting AEs

- Analysis time points: Dose 1 to 1 month after Dose 3, and from Dose 4 to 1 month after Dose 4
- Analysis population: Dose 1 to Dose 3 safety population, Dose 4 safety population.
- Analysis methodology: Descriptive statistics
- Supporting objective: Primary Objective

Reporting results:

The percentage (%), number of subjects and the denominator (N) used in the percentage calculation, and corresponding 95% Clopper-Pearson CI will be presented for each vaccine group.

Figures: None

6.1.4. Serious Adverse Events and Newly Diagnosed Chronic Medical Conditions

6.1.4.1. Primary Analysis

Endpoint: Proportions of subjects reporting SAEs and NDCMCs

- Analysis time points: Dose 1 to 6 months after Dose 4
- Analysis population: Safety analysis population
- Analysis methodology: Descriptive statistics
- Supporting objective: Primary Objective

Reporting results:

The percentage (%), number of subjects and the denominator (N) used in the percentage calculation, and corresponding 95% Clopper-Pearson CI will be presented for each vaccine group.

Figures: None

6.2. Secondary Endpoints

The ordering of the pneumococcal serotypes in summaries will be as follows and will appear on the same table:

- 13vPnC serotypes: 1, 3, 4, 5, 6A, 6B, 7F, 9V, 14, 18C, 19A, 19F, 23F; and
- Additional Serotypes: 8, 10A, 11A, 12F, 15B, 22F, 33F.

6.2.1. Pneumococcal Serotype-specific Immunoglobulin G (IgG) Concentrations 1 Month after Dose 3

Endpoint: Pneumococcal serotype-specific IgG concentrations 1 month after Dose 3

- Time points: 1 month after Dose 3
- Analysis population: Dose 3 evaluable immunogenicity
- Analysis methodology: Descriptive statistics
- Supporting objective: Secondary Objective

Reporting results:

IgG GMCs with their associated 95% CIs will be summarized separately at 1 month after Dose 3 for each pneumococcal serotype by each vaccine group.

The percentage (%) and the number of subjects with serotype-specific IgG concentrations \geq reference concentrations (n) and the denominator (N) used in the percentage calculation, and corresponding 95% Clopper-Pearson CI will be presented for each vaccine group 1 month after Dose 3.

6.2.2. Pneumococcal Serotype-specific Immunoglobulin G (IgG) Concentrations 1 Month after Dose 4

[figure not shown]
Endpoint: Pneumococcal serotype-specific IgG concentrations 1 month after Dose 4

[figure not shown]
- Time points: 1 month after Dose 4
- Analysis population: Dose 4 evaluable immunogenicity CCI
- Analysis methodology: Descriptive statistics
- Supporting objective: Secondary Objective

Reporting results:

IgG GMCs with their associated 95% CIs will be summarized separately at 1 month after Dose 4 for each pneumococcal serotype by each vaccine group.

6.5. Baseline and Other Summaries and Analyses

6.5.1. Study Conduct and Subject Disposition

6.5.1.1. Subject Disposition

Disposition of subjects relative to Dose 1 to Dose 3 will be summarized for all subjects as follows: The number of consented subjects and the number and percentage of randomized subjects who are randomized, receive each vaccination (Dose 1, Dose 2, Dose 3), complete Dose 1 to Dose 3, withdraw during Dose 1 to Dose 3 and the specific reasons (LAR request, lost to follow-up, failed to return, adverse event, protocol violation, other) will be summarized by vaccine group (according to randomized group assignment). A similar summarization of disposition relative to Dose 4 will also be prepared, including the number and percentage of randomized subjects who completed through 1 month after Dose 3,

withdrew after 1 month after Dose 3 but prior to Dose 4 by reason, received Dose 4, and withdrew after Dose 4 but before blood draw 1 month after Dose 4 by reason.

The number of consented subjects and the number and percentage of randomized subjects who are randomized, vaccinated, completed, and withdrawn through 1 month after Dose 4 will be presented for each vaccine group (according to randomized group assignment) and overall.

The above information will also summarized for the time period from 1 month after Dose 4 through 6 months after Dose 4.

CCI

